8.2.1 Solicited Events

Solicited events are AEs that are common and known to occur following administration of study product.

8.2.2 Unsolicited Events

Unsolicited events are any other AEs that occur following administration of study product.

8.2.3 New Onset Chronic Medical Conditions (NOCMCs)

NOCMCs are defined as any new ICD-10 that is applied to the subject during the duration of the study, after receipt of the study agent, that is expected to continue for at least 3 months and requires continued health care intervention.

8.2.4 Medically Attended Adverse Events (MAAEs)

For each unsolicited AE experienced, the subject will be asked if he/she had received medical attention, defined as hospitalization, an emergency room visit, or an otherwise unscheduled visit to or from medical personnel for any reason. AEs characterized by such unscheduled medical care will be designated as MAAEs.

8.2.5 Potentially Immune Mediated Medical Conditions (PIMMCs)

PIMMCs constitute a group of AEs that includes diseases which are clearly autoimmune in etiology and other inflammatory and/or neurologic disorders which may or may not have autoimmune etiologies. PIMMCs currently in effect are presented in [APPENDIX B. LIST OF POTENTIALLY IMMUNE MEDIATED MEDICAL CONDITIONS](#)

8.3 Reporting Procedures

Solicited injection site and systemic reactogenicity events will be documented and reported from the time of each study vaccination through 7 days after each study vaccination.

Clinical safety laboratory AEs will be documented and reported from the time of each study vaccination through approximately 7 days after each study vaccination.

Unsolicited non-serious AEs will be documented and reported from the time of each study vaccination through approximately 21 days after each study vaccination.

SAEs, MAAEs, including NOCMCs, and PIMMCs will be documented and reported from the time of the first study vaccination through approximately 12 months after the last study vaccination.

8.3.1 Reporting Serious Adverse Events

SAEs will be followed until resolution even if this extends beyond the study-reporting period. Resolution of an AE is defined as the return to pretreatment status or stabilization of the condition with the expectation that it will remain chronic.

Any AE that meets a protocol-defined serious criterion must be submitted immediately (within 24 hours of site awareness) on an SAE form to the DMID Pharmacovigilance Group at the following address:

**DMID Pharmacovigilance Group
Clinical Research Operations and Management Support (CROMS)
[name]
[name]**

In addition to the SAE form, selected SAE data fields must also be entered into the DCC system (for example AdvantageEDC). Please see the protocol-specific MOP for details regarding this procedure.

Other supporting documentation of the event may be requested by the DMID Pharmacovigilance Group and should be provided as soon as possible.

The site will send a copy of the SAE report(s) to the ISM (as deemed necessary) when they are provided to the DMID Pharmacovigilance Group. The DMID Medical Monitor and DMID Clinical Project Manager will be notified of the SAE by the DMID Pharmacovigilance Group. The DMID Medical Monitor will review and assess the SAE for regulatory reporting and potential impact on study subject safety and protocol conduct.

At any time after completion of this trial, if the site PI or appropriate sub-investigator becomes aware of an SAE that is suspected to be related to study product, the site PI or appropriate sub-investigator will report the event to the DMID Pharmacovigilance Group.

8.3.2 Regulatory Reporting for Studies Conducted Under DMID Sponsored IND

Following notification from the investigator, DMID, the Investigational New Drug (IND) sponsor, will report any suspected adverse reaction that is both serious and unexpected. DMID will report an AE as a suspected adverse reaction only if there is evidence to suggest a causal relationship between the drug and the AE. DMID will notify FDA and all participating site investigators (i.e., all investigators to whom the sponsor is providing drug under its IND(s) or under any PI's IND(s)) in an IND safety report of potential serious risks from clinical trials or any other source, as soon as possible, but in no case later than 15 calendar days after the sponsor determines that the information qualifies for reporting as specified in 21 CFR Part 312.32. DMID will also notify FDA of any unexpected fatal or life-threatening suspected adverse reaction as soon as possible, but in no case later than 7 calendar days after the sponsor's initial receipt of the information. Relevant follow up information to an IND safety report will be submitted as soon as the information is available. Upon request from FDA, DMID will submit to FDA any additional data or information that the agency deems necessary, as soon as possible, but in no case later than 15 calendar days after receiving the request.

All serious events designated as “not related” to study product(s), will be reported to the FDA at least annually in a summary format.

8.3.3 Reporting of Pregnancy

Pregnancies occurring in study subjects will be reported via AdvantageEDCSM on the Pregnancy Report form. No further study vaccinations will be administered to pregnant subjects, but with the subject's permission all protocol-required venous blood samples will be obtained and the subject will continue to be followed for safety for the duration of this trial. Efforts will be made to follow all pregnancies reported during the course of this trial to pregnancy outcome pending the subject's permission.

8.3.4 Disclosure of Study Related Information

Subjects can choose to receive written disclosure of their treatment assignment after the database has been locked.

8.4 Type and Duration of Follow-up of Subjects after Adverse Events

AEs will be collected, assessed, and followed through resolution from the time of each study vaccination through approximately 21 days after each study vaccination.

SAEs, MAAEs, including NOCMCs, and PIMMCs will be collected, assessed, and followed from the time of the first study vaccination through resolution even if this extends beyond the trial-reporting period (approximately 12 months after the last study vaccination).

Resolution of an AE/SAE is defined as the return to pretreatment status or stabilization of the condition with the expectation that it will remain chronic.

Follow-up procedures, evaluations, and outcomes will be recorded on the appropriate data collection form.

8.5 Procedures to be Followed in the Event of Abnormal Laboratory Test Values or Abnormal Clinical Findings

The site PI or appropriate sub-investigator is responsible for recording all AE/SAEs that are observed or reported during this trial, regardless of the relationship to study product. AE/SAEs, abnormal laboratory test values, or abnormal clinical findings will be collected, assessed, documented, reported, and followed appropriately, using a local laboratory as necessary. In determining eligibility, refer to [section 5.1](#) and the protocol-specific MOP.

Clinical safety laboratory results[#] will be graded as follows:

Clinical Safety Laboratory Adverse Event Grading[#]

Hematology	Mild (Grade 1)	Moderate (Grade 2)	Severe (Grade 3)
WBC 10 ³ /μL (Decrease)	2.5 – 3.9	1.5 – 2.4	<1.5
WBC 10 ³ /μL (Increase)	10.6 – 15.0	15.1 – 20.0	>20.0
Hgb g/dL (Decrease) (Female)	10.1 – 11.4	8.5 – 10	<8.5
Hgb g/dL (Decrease) (Male)	11.0 – 12.4	9.5 – 10.9	<9.5
Platelets 10 ³ /μL (Decrease)	125 – 139	100 – 124	<100
Platelets 10 ³ /μL (Increase)	416 – 550	551 – 750	>750

Chemistry	Mild (Grade 1)	Moderate (Grade 2)	Severe (Grade 3)
ALT IU/L (Increase) (Female)	44 – 100	101 – 200	>200
ALT IU/L (Increase) (Male)	61 – 138	139 – 275	>275
Total Bilirubin mg/dL (Increase) – when accompanied by any increase in ALT	1.30 – 1.59	1.60 – 1.80	>1.80

Total Bilirubin mg/dL (Increase) – when ALT is normal	1.30 – 1.89	1.90 – 2.40	>2.40
Creatinine mg/dL (Increase) (Female)	1.1 – 1.7	1.8 – 2.0	>2.0
Creatinine mg/dL (Increase) (Male)	1.4 – 1.7	1.8 – 2.0	>2.0

Clinical laboratory evaluations assessed on Day 1 prior to the first study vaccination will be considered as baseline.

8.6 Halting Rules

8.6.1 Study Halting Criteria

Further enrollment and study vaccinations will be halted for DSMB review/recommendation if any of the following are reported:

- Any subject experiences ulceration, abscess, or necrosis at the injection site related to study product administration.
- Any 2 or more subjects experience laryngospasm, bronchospasm, or anaphylaxis within 1 day after administration of study product that is considered related to study product.
- Three or more subjects experience generalized urticaria (defined as occurring at more than two body parts) within 3 days after administration of study product that is considered related to study product.
- Any subject experiences a study vaccine-related SAE from the time of the first study vaccination through the subject’s last study visit.
- Any subject experiences acute weakness of limbs and/or cranial nerve innervated muscles (description of potential signal of GBS) after administration of study product.
- Any subject develops a PIMMC after administration of study product.

This trial will also be halted for DSMB review/recommendation if, within 7 days after administration of either study vaccination, any of the following occurs within the MF59[®]-adjuvanted treatment arms or within the one unadjuvanted treatment arm.

- 7% or more of subjects (with a minimum of 3 subjects) who received at least one dose of study vaccine to date, cumulative to both vaccine administrations, across all groups, experience the same severe (Grade 3) study vaccine-related injection site reaction.

Ecchymosis, erythema, and induration/swelling will also be measured in mm but size will not be used as halting criteria.

- 7% or more of subjects (with a minimum of 3 subjects) who received at least one dose of study vaccine to date, cumulative to both vaccine administrations, across all groups, experience the same severe (Grade 3) study vaccine-related subjective systemic reaction, for which the severity (grade) is corroborated by study personnel.
- 7% or more of subjects (with a minimum of 3 subjects) who received at least one dose of study vaccine to date, cumulative to both vaccine administrations, across all groups, experience the same severe (Grade 3) study vaccine-related quantitative systemic reaction.
- 7% or more of subjects (with a minimum of 3 subjects) who received at least one dose of study vaccine to date, cumulative to both vaccine administrations, across all groups, experience the same severe (Grade 3) study vaccine-related clinical safety laboratory AE.

Grading scales for solicited injection site and systemic (subjective and quantitative) reactions are included in [Section 8.1.2](#).

Grading scales for clinical safety laboratory AEs are included in [Section 8.5](#).

If any of the halting rules are met following any subject receipt of any study vaccination, then this trial will not continue with the remaining enrollments or study vaccinations without a review by and recommendation from the DSMB to proceed.

DMID retains the authority to suspend additional enrollment and study interventions/ administration of study product during the entire trial, as applicable.

The DMID Medical Monitor is empowered to stop enrollment and study vaccinations if AEs that meet the halting criteria are reported.

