6.4 Planned Study Visits

6.4.1 Follow-up

Follow-up visits are scheduled in reference to study vaccination dates as indicated for each visit window.

Visit 02, Day 4, Memory Aid Review, Phone Call (Window: Day 4±1 days post first study vaccination)

Study personnel will contact subjects by phone to solicit any AEs/SAEs/MAAEs/NOCMCs/PIMMCs, medical history, and concomitant medication information and review information on their Memory Aid. Based on the information, subjects may be asked to return to the clinic for evaluation.

Visit 03, Day 8, Clinic Visit (Window: Day 8±2 days post first study vaccination)

- Interim medical history, including an assessment for new medical conditions, stability of chronic diseases, and symptoms suggestive of PIMMCs, will be obtained by interview of subjects and any changes since the previous clinic visit or contact will be noted.
- Memory Aid information will be reviewed with subjects.

- All concomitant medications (including solicitation for receipt of any non-study influenza vaccines), including those that are experimental, what type (inactivated or live attenuated), what subtype (e.g., A/H3, A/H5, A/H9) and approximate date of vaccination will be recorded on the appropriate DCF, if known and not previously collected).
- All AE/SAEs/MAAEs/NOCMCs/PIMMCs will be recorded on the appropriate data collection form.
- A targeted physical examination, including an assessment for signs suggestive of PIMMCs, may be performed, if indicated based on review of interim medical history, by a study clinician licensed to make medical diagnoses and listed on the Form FDA 1572 as the site PI or sub-investigator.
- The first study vaccination site will be examined.
- Approximately 10 mL of venous blood will be collected for clinical safety labs (WBC, Hgb, PLT, ALT, T. Bili, Cr), and performed by the central (clinical) laboratory.
- Approximately 10 mL of venous blood will be collected for serum antibody assays.
- Approximately 10 mL of venous blood will be collected for future research from subjects who consent to collection of serum for future use either by signing an ICF that includes collection of future use samples as a condition of study participation or by indicating that they can opt in to sample collection for future use if the ICF allows the option to choose that option.

**Visit 04, Day 22, Second Study Vaccination (Dose 2), Clinic Visit
(Window: Day 22+7 days post first study vaccination)**

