- Subjects will be provided with a Memory Aid and other study-related materials to record daily oral temperature, solicited injection site and systemic reactions, any unsolicited AEs, and concomitant medications. Subjects will be encouraged to take their oral temperature around the same time each day. Subjects must not eat or drink anything hot or cold, or smoke within 10 minutes prior to taking oral temperature. Subjects will be instructed on how to use their Memory Aid and how to measure and record AEs prior to discharge from the clinic. Subjects will be instructed to notify the study center if they develop any severe reactions after the second study vaccination. If the site PI or appropriate sub-investigator deems the reaction severe enough, further instructions will be given to the subject on the proper course of action, including a return to the clinic for immediate evaluation if appropriate.

Visit 05, Day 25, Memory Aid Review, Phone Call
(Window: Day 4 ±1 days post second study vaccination)

Study personnel will contact subjects by phone to solicit any AE/SAE, medical history, and concomitant medication information (including solicitation for receipt of any non-study influenza vaccines), including those that are experimental, what type (inactivated or live attenuated), what subtype (e.g., A/H3, A/H5, A/H9) and approximate date of vaccination will be recorded on the appropriate DCF, if known and not previously collected) and review information on their Memory Aid. Based on the information, subjects may be asked to return to the clinic for evaluation. Note: For subjects who are discontinued from the receipt of the second study vaccination, AEs will be limited to SAEs, MAAEs, including NOCMCs, and PIMMCs.

Visit 06, Day 29, Clinic Visit
(Window: Day 8±2 days post second study vaccination)

- Interim medical history, including an assessment for new medical conditions, stability of chronic diseases, and symptoms suggestive of PIMMCs, will be obtained by interview of subjects and any changes since the previous clinic visit or contact will be noted.

- Memory Aid information will be reviewed with subjects.
- All concomitant medications (including solicitation for receipt of any non-study influenza vaccines), including those that are experimental, what type (inactivated or live attenuated), what subtype (e.g., A/H3, A/H5, A/H9) and approximate date of vaccination will be recorded on the appropriate DCF, if known and not previously collected).

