8.7.2 Data and Safety Monitoring Board (DSMB)

Safety oversight will be conducted by a DSMB that is an independent group of experts that monitors subject safety and advises DMID. The DSMB members will be separate and independent of study personnel participating in this trial and should not have scientific, financial or other conflict of interest related to this trial. The DSMB will consist of members with appropriate expertise to contribute to the interpretation of the data from this trial. The DSMB will operate under the rules of a DMID-approved charter that will be written at the organizational meeting of the DSMB. Procedures for DSMB reviews/meetings will be defined in the charter. Reports may include enrollment and demographic information, medical history, concomitant medications, physical assessments, clinical laboratory values, dosing compliance, and solicited and unsolicited AE/SAEs, HAI and Neut antibody assay results. The DSMB will review SAEs on a regular basis and ad hoc during this trial. The DMID Medical Monitor and the ISM (as deemed necessary) will be responsible for reviewing SAEs in real time.

The DSMB will conduct the following reviews:

- Bi-monthly (every two months) safety data reviews (including monthly safety data and cumulative safety data) until the last subject completes the visit that occurs approximately 21 days after the last study vaccination.
- Data review 9 days after all subjects have received Dose 2 (complete study visit number V06). This review may be conducted as part of the scheduled monthly reviews.
- Ad hoc when a halting rule is met or DMID/DSMB chair may convene an ad hoc meeting if there are immediate concerns regarding observations during the course of this trial.

- Final review meeting: 6 to 8 months after clinical database lock to review the cumulative unblinded safety and immunogenicity data for this trial. The data will be provided in a standard summary format. The DSMB may be asked to provide recommendations in response to questions posed by DMID.

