4.4.5. Selection and Timing of Dose for Each Subject

Each subject is to be randomly assigned to a study group which will define the A/H7N9 vaccine dose and receipt of adjuvant for both planned study vaccinations. The first vaccination takes place on the day of randomization, and the second vaccination takes place approximately 21 days after the first vaccination (protocol defined window of 21-28 days post first vaccination).

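### The 7% laboratory halting rule stops at 7 days after vaccination, but the safety draws that feed it may be taken up to 9 days after

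*Protocol*

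**What the plan says.** Protocol 8.6.1 lists four criteria, each triggered when at least 7% of subjects, and no fewer than 3, have the same related Grade 3 event. All four sit under one lead-in: "This trial will also be halted for DSMB review/recommendation if, within 7 days after administration of either study vaccination". The fourth concerns subjects who "experience the same severe (Grade 3) study vaccine-related clinical safety laboratory AE". Its denominator is everyone "who received at least one dose of study vaccine to date, cumulative to both vaccine administrations".

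Section 6.4.1 schedules the post-dose safety draws at two visits: V03 ("Window: Day 8±2 days post first study vaccination") and V06 ("Window: Day 8±2 days post second study vaccination"). Table 2 and Appendix A print the window as D8+2d. The lower limit differs, but both versions end on Day 10.

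Elsewhere (3.3.1, 8.1, 8.3) the protocol ends the laboratory AE period at about 7 days after each vaccination. The halting text does not carry that qualifier.

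**The concern.** The time limit suits the three solicited-reaction rules, because solicited reactions are collected for exactly 7 days. It does not suit the laboratory rule, whose scheduled data can properly arrive later. A subject drawn on Day 9 or Day 10 complies with the visit schedule. If that draw shows a related Grade 3 value, the literal rule ignores it but still counts the subject as dosed.

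The error runs one way: the observed percentage can only be too low. At stake is one automatic pause in a trial of a vaccine that, by Protocol 2.3.1, had been tested neither for safety in animals nor in humans.

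**Working it through.** **Day numbering.** Days after dosing = Day − 1. The visit schedule confirms this, with dose 2 on Day 22: V05 = 22 + 3 = 25, V06 = 22 + 7 = 29, V07 = 22 + 21 = 43. SAP 4.4.5 agrees, giving Day 22+7 as a "protocol defined window of 21-28 days post first vaccination".

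**The plan's own figure.** The upper end of the V06 window is Day 8 + 2 = Day 10, and 10 − 1 = 9 days after dose 2. Protocol 8.7.2 gives the same number: "Data review 9 days after all subjects have received Dose 2 (complete study visit number V06".

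**Which draws count under a literal reading.**

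| Day of draw | Days after dosing | Within 7 days? |
|---|---|---|
| 6, 7, 8 | 5, 6, 7 | yes |
| 9, 10 | 8, 9 | no |

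Two of the five permitted days fall outside the rule under Day 8±2, and two of three under D8+2d.

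**Threshold.** c(n) = max(3, ⌈0.07n⌉). This gives 3 at n = 42, 4 at 53, 7 at 100, 8 at 106, 23 at 318 and 26 at 371. One excluded result can decide the matter: 7/100 = 7.0% halts and 6/100 does not; 26/371 = 7.01% halts and 25/371 = 6.7% does not.

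**Chance of triggering.** The plan states no operating characteristics for this rule, so the following is illustrative. Let p be the true rate of the same related Grade 3 laboratory AE, and f the share of draws taken at 8–9 days. Both are assumptions. Each subject is given one countable draw, so q = p(1 − f). For n = 1 to 318 (3 × 106 adjuvanted subjects), with no reporting lag, carry forward

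P(n, k) = P(n−1, k)(1 − q) + P(n−1, k−1)q,

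and move to *triggered* any probability with k ≥ c(n).

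| Scenario | f = 0 | f = 10% | f = 20% | f = 40% |
|---|---|---|---|---|
| p = 10%, checked after every subject | 99.5% | 98.2% | 94.4% | 71.5% |
| Subject by which half of trials have triggered | 27 | 30 | 34 | 53 |
| p = 10%, checked every 25 subjects and at 318 | 99.2% | 97.2% | 91.7% | 62.2% |
| p = 15%, every subject | 100% | 100% | >99.9% | 98.2% |
| p = 8%, every subject | 94.4% | 88.1% | 78.0% | 48.5% |
| p = 7%, every subject | 86.0% | 76.4% | 64.2% | 36.8% |
| p = 10%, recurs after both doses, q = p(1 − f²) | 99.5% | 99.5% | 99.2% | 96.4% |
| p = 10%, unadjuvanted arm alone (53) | 84.9% | 78.9% | 71.2% | 50.7% |

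The recurrence row assumes independent draw timing after the two doses, counts each subject once, and ignores the roughly 3-week gap between draws. The f = 40% column is an even spread over Day 8±2 (2 of 5 days); no document supports it.

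**A different look.** A single check at all 371 subjects (threshold 26) with p = 10% gives 98%, 93%, 67% and 23% at f = 0, 10%, 25% and 40%.

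**The case against.** **It may be only a missing word.** The laboratory AE is described in three places as running to about 7 days, and the draws are described the same way. On that reading an in-window V03 or V06 result already counts. This is probably what the authors meant, and nothing shows that any monitor applies the strict limit. But 8.6.1 sets its own limit without the qualifier, and a mandatory trigger should not depend on inference from other sections.

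**The limit is on when the event occurs, not when blood is drawn.** A Grade 3 value found at 8–9 days may have begun earlier. True, but 8.6.1 does not say how to date an event whose first evidence is the draw. Leaving that to each site is part of the ambiguity.

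**A time limit is a legitimate choice.** The V04 pre-dose draw, 21–28 days after dose 1, is also excluded on the literal reading. That exclusion can be defended, because V04 is not the scheduled 7-day check. V03 and V06 are.

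**The size is assumed.** This stands. The documents give neither p nor f. The loss at f = 10–20% is about 1–5 points at p = 10%, but about 10–22 points at p = 7% and 1.5–3 points at p = 2%. Section 8.6.1 also refers both to the adjuvanted arms and to all groups, so the denominator is itself unsettled.

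**Other safeguards exist.** This largely stands and is why severity is low, but none is a substitute.
- The related-SAE and PIMMC rules do not catch a non-serious laboratory value.
- The individual rule in 8.6.2 protects one subject before dose 2 and cannot act on V06 results.
- Scheduled DSMB reviews come every two months, against about 12 weeks of enrolment, and the V06-linked review follows the last second dose.
- The Medical Monitor's power refers to AEs that meet the halting criteria, so it inherits the gap.
- The sponsor's power ("DMID retains the authority to suspend additional enrollment") is broad but discretionary.

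**Conclusion.** The concern holds as a wording gap in a safety trigger. Taken as written, 8.6.1 omits compliant laboratory results from 8 and 9 days after dosing. That conclusion needs only the day arithmetic and the text, not the simulated probabilities.

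The practical effect is small to moderate. It is negligible if the true rate is well above 7% (at 15%, essentially none up to f = 20%) or if the abnormality recurs after both doses. It is largest when the rate is close to the threshold. These sizes rest on assumed values of p and f, one countable draw per subject except in the recurrence row, and no reporting lag. This is worth correcting, but it is not a reason to doubt the trial's overall safety oversight.

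**What to change.** In Protocol 8.6.1, for the laboratory criterion only, replace the 7-day limit with a visit-based one. Count related Grade 3 results from the V03 or V06 safety draw taken within its protocol window (through Day 10, 9 days after that dose), plus any earlier unscheduled or early-termination draw after that dose. Leave the 7% threshold, the minimum of 3 subjects and the 7-day limit for solicited reactions as they are.

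The cost is one clause in the protocol and the same definition wherever the rule is monitored. It needs no extra visits or samples.

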There is potential for AEs to occur more frequently in the adjuvanted vaccine groups [32] than in the non-adjuvanted group and there is potentially a higher risk for AEs to occur more frequently in the higher dose influenza antigen groups than in the lower dose viral antigen groups. The 2017 H7N9 IIV to be used in this study has not been tested for safety in animals and has not previously been evaluated in humans. The DMID, NIAID has sponsored five Phase II clinical trials to assess the safety, reactogenicity, and immunogenicity of one or two IM doses of a monovalent A/H7N9 vaccine produced by Sanofi Pasteur, Swiftwater, PA, administered with or without AS03 or MF59[®] in healthy subjects (DMID Protocols: 13-0032, NCT01938742; 13-0033, NCT01942265; 13-0034, NCT02213354; 13-0044, NCT02586792; and 14-0015, NCT02921997). Overall, the study products administered in these clinical trials were generally safe and well-tolerated. For DMID Protocol 13-0032, nine SAEs were reported. All were assessed as being not related to study product. Two AEs of special interest (AESIs) were reported in this clinical trial: Hashimoto's disease (assessed as not related to study product) and Hashimoto's thyroiditis (assessed as related to study product). For DMID Protocol 13-0033, sixteen SAEs were reported, fifteen of these SAEs were assessed as being not related to study product. One SAE was considered to be related: acute inferior myocardial infarction. Two AESIs were reported in this clinical trial: psoriasiform dermatitis and celiac disease (both assessed as not related to study product because both disorders pre-existed to vaccination, but both disorders received the diagnosis after vaccination).

The manufacturing process used to produce the monovalent 2017 H7N9 IIV is the same as for the US licensed product Agriflu[®] seasonal influenza vaccine with the exception of the final steps being performed at the Parkville manufacturing site, which is an FDA-approved manufacturing site for Afluria[®], but not Agriflu[®]. The current H7N9 monovalent subunit IIV to be used in this trial was derived from the influenza virus A/Hong Kong/125/2017 (H7N9). The potential risks to subjects are anticipated to be similar to those observed for Seqirus' unadjuvanted, licensed seasonal IIV, Agriflu[®] (see Agriflu[®] Package Insert).

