Additional data may be requested by the DSMB, and interim statistical reports may be generated as deemed necessary and appropriate by DMID. The DSMB may receive data in aggregate and presented by treatment arm. The DSMB may also be provided with expected and observed rates of the expected AEs in an unblinded fashion, and may request the treatment assignment be unblinded for an individual subject if required for safety assessment. The DSMB will review grouped and unblinded data in the closed session only. As an outcome of each review/meeting, the DSMB will make a recommendation as to the advisability of proceeding with study vaccinations (as applicable), and to continue, modify, or terminate this trial.

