6.6.1. Interim Safety Review

An interim safety review may include enrollment and demographic information, medical history, concomitant medications, physical assessments, clinical laboratory values, dosing compliance, and solicited and unsolicited AE/SAEs. Additional data may be requested by the DSMB, and interim statistical reports may be generated as deemed necessary and appropriate by DMID. The DSMB may receive data in aggregate and presented by study arm. The DSMB may also be provided with expected and observed rates of the expected AEs in an unblinded fashion and may request the treatment assignment be unblinded for an individual subject if required for safety assessment. The DSMB will review grouped and unblinded data in the closed session only. The DSMB will meet and review this data at scheduled time points or ad hoc as needed during this trial as defined in the DSMB charter. As an outcome of each review/meeting, the DSMB will make a recommendation as to the advisability of proceeding with study vaccinations (as applicable), and to continue, modify, or terminate this trial. Summaries prepared for the DSMB are defined separately in a report shell reviewed and approved by the DSMB.

Additionally, this trial will be monitored to determine if any of the halting rules described in Protocol Section 9.5 are met.

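### Protocol 8.6.1 gives two conflicting populations for its 7% halting rule, so the number of Grade 3 cases that stops the trial depends on the reading

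*Protocol*

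**What the plan says.** Protocol 8.6.1 has two sets of study-level halting criteria. The first is count-based: one, two or three subjects with specified events. The second is the only percentage-based rule, and it covers the 7 days after either vaccination.

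- **Lead-in.** The trial halts for DSMB review if a listed event occurs within the MF59-adjuvanted "treatment arms or within the one unadjuvanted treatment arm".
- **Bullets.** Four bullets follow: injection site, subjective systemic, quantitative systemic and laboratory. Each sets a threshold of 7% or more, with a minimum of 3 subjects, among subjects "who received at least one dose of study vaccine to date, cumulative to both vaccine administrations, across all groups". The laboratory bullet, for example, reads "across all groups, experience the same severe (Grade 3) study vaccine-related clinical safety laboratory AE".

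The rule is binding: once it is met, enrolment and vaccination may not go on until the DSMB has reviewed and recommended proceeding.

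Protocol 10.4.1 only refers back to 8.6.1. SAP 6.6.1 restates no rule or denominator and says "this trial will be monitored to determine if any of the halting rules described in Protocol Section 9.5 are met". Protocol 9.5 is Subject Confidentiality.

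**The concern.** The lead-in assesses populations separately, while the bullets pool everyone dosed. Both cannot define the same percentage. At least three readings are open:

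1. all four groups pooled;
2. the three adjuvanted arms pooled, with the unadjuvanted arm assessed on its own;
3. each adjuvanted arm separately, with the unadjuvanted arm assessed on its own.

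At stake is when dosing pauses for related Grade 3 reactions or laboratory events, with a vaccine that Protocol 2.3.1 says has not been evaluated in humans before. Two careful readers could reach opposite mandatory actions from the same data. The readings also differ in operation: 2 and 3 need treatment allocation in a double-blind trial, and 1 does not.

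**Working it through.** **Inputs.** The threshold is 7% with a minimum of 3 (Protocol 8.6.1). Planned arm sizes are 106, 106, 106 and 53 (Protocol 10.2), so the adjuvanted total is 3 × 106 = 318 and the overall total is 318 + 53 = 371. Both totals appear in the protocol. Allocation is 2:2:2:1 (Protocol 10.3.1). The documents state no trigger count, so there is no figure to reproduce.

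**Formula.** Trigger = max(3, 0.07 × N rounded up), where N is the number dosed to date in the population assessed.

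**At full enrolment**

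| Population | N | 0.07 × N | Trigger |
|---|---|---|---|
| All groups | 371 | 25.97 | 26 |
| Adjuvanted arms pooled | 318 | 22.26 | 23 |
| One adjuvanted arm | 106 | 7.42 | 8 |
| Unadjuvanted arm | 53 | 3.71 | 4 |

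**During enrolment.** With 210 dosed (60:60:60:30) the triggers are 15 of 210, 13 of 180, 5 of 60 and 3 of 30.

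**Data on which the readings disagree**

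- 23 to 25 cases, all in adjuvanted arms: 23/318 = 7.2% to 25/318 = 7.9% (halt), but 23/371 = 6.2% to 25/371 = 6.7% (no halt).
- 4 cases, all in the unadjuvanted arm: 4/53 = 7.5% (halt), but 4/371 = 1.1% (no halt).
- 8 cases, all in one adjuvanted arm: 8/106 = 7.5% (halt if arms are separate), but 8/318 = 2.5% and 8/371 = 2.2% (no halt).
- The reverse, with 105 dosed (30:30:30:15) and 2 cases in every arm: 8/105 = 7.6% meets the all-groups trigger of 8. But 6/90 = 6.7% is below 7%, 2/30 = 6.7% is below 7%, and 2 of 15 is below the minimum of 3, so no by-arm reading triggers.

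No reading is therefore always the more cautious one.

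**Illustrative probabilities.** The documents give no Grade 3 rates, so these rates are assumptions: 1% in the unadjuvanted arm and a rate p in each adjuvanted arm. The direction follows Protocol 2.3.1: "There is potential for AEs to occur more frequently in the adjuvanted vaccine groups". The values are exact binomial tails at one look at full enrolment:

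- adjuvanted pooled: P(Bin(318, p) ≥ 23);
- all groups: P(Bin(318, p) + Bin(53, 0.01) ≥ 26);
- any single adjuvanted arm: 1 − (1 − P(Bin(106, p) ≥ 8))³.

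| p | Adjuvanted pooled | All groups | Any one adjuvanted arm |
|---|---|---|---|
| 3% | 0.0001 | 0.00001 | 0.04 |
| 4% | 0.005 | 0.001 | 0.18 |
| 5% | 0.05 | 0.015 | 0.41 |
| 8% | 0.72 | 0.53 | 0.95 |
| 10% | 0.96 | 0.90 | >0.99 |

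At p = 8% with 210 dosed, P(Bin(180, 0.08) ≥ 13) = 0.69 for adjuvanted pooled, against P(Bin(180, 0.08) + Bin(30, 0.01) ≥ 15) = 0.51 for all groups.

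**The case against.** The strongest reply is that the phrase about all groups means pooling within whichever population the lead-in names. That is possible, but the text does not say so, and the words would then mean nothing for a single unadjuvanted arm.

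Other objections carry some weight:

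- **The separate-arm reading is the weakest.** The lead-in sets the adjuvanted arms, in the plural, against the one unadjuvanted arm, and Protocol 10.2 itself pools adjuvanted recipients at 318. This stands: the figures for 106 should carry least weight.
- **The gap between the two main pooled readings is small early on.** The adjuvanted-pooled and all-groups triggers are 3 and 3 with 42 dosed, 6 and 6 with 84, and 7 and 8 with 105. This also stands, although equal triggers applied to different populations can still give different answers. The unadjuvanted arm's trigger differs far more, but at an assumed 1% rate that arm would trigger with probability only 0.002.
- **The probabilities depend on rates near 7%.** At 3% or 4% a trigger is unlikely on either pooled reading, and Protocol 2.3.1 expects mostly mild or moderate reactions. A single look at full enrolment is also not the chance of halting during the trial. Both points limit the illustration, but the conflict does not depend on it.
- **There are backstops.** The count-based rules apply regardless. Protocol 8.6.2 withholds the second dose from individuals with specified Grade 3 events. "DMID retains the authority to suspend additional enrollment", and "The DSMB may receive data in aggregate and presented by treatment arm". DSMB review takes place every two months and after Visit 06, and also "Ad hoc when a halting rule is met or DMID/DSMB chair may convene an ad hoc meeting if there are immediate concerns". But sponsor suspension and concern-driven meetings are discretionary, and a meeting called because a rule is met presupposes knowing whether it is met.
- **The DSMB charter and report shell may settle the matter.** They were not available, so the finding is confined to the protocol and SAP.

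**Conclusion.** The concern holds. The lead-in and all four bullets of the 7% rule define different populations, and nothing in the protocol or SAP resolves the difference. At full planned enrolment the trigger is 26, 23 or 4 subjects depending on the population, or 8 if adjuvanted arms are taken singly. The same data can require a halt on one reading and not on another, in either direction. These counts rest only on the planned arm sizes and the stated 7% and minimum of 3; the probabilities rest on assumed rates and serve only to illustrate. Because this is a binding safety threshold, it must be fixed. The SAP's wrong section reference is a minor clerical error and adds no weight.

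**What to change.** The sponsor and DSMB should reconcile the lead-in of Protocol 8.6.1 with its four 7% bullets, so that the population and denominator are stated once and consistently. If the rule is assessed by arm, the text should also say whether the adjuvanted arms are pooled or separate. Which scope to adopt is for the sponsor and DSMB; this review does not propose one. The DSMB charter and report shell should be checked against the clarified wording.

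In SAP 6.6.1, change the reference from Protocol Section 9.5 to Section 8.6.1, which Protocol 10.4.1 already cites correctly.

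The cost is roughly one sentence of protocol clarification and one SAP correction. No further subjects or data are needed.
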